13.0 CRITERIA FOR REMOVAL FROM STUDY

If at any time the patient develops progressive disease he/she will be taken off study.

If at any time the patient refuses to comply with study procedures or withdraws informed consent, he/she will be taken off study.

If at any time the patient develops unacceptable toxicity he/she will be removed from study.

If at anytime the patient is found to be ineligible for the protocol as designated in the section on Criteria for Patient/Subject Eligibility (i.e., a change in diagnosis), the patient will be removed from the study.

14.0 BIOSTATISTICS

This is a double-blinded, randomized phase II trial assessing the efficacy of vaccination with the WT-1 vaccine plus the immunologic adjuvant Montanide ISA 51 VG plus GM-CSF (Arm A) to non-specific immune stimulation with Montanide and GM-CSF alone as a control (Arm B) in patients who have completed multimodality therapy including surgery (plus at least one of chemotherapy and radiation) for malignant pleural mesothelioma. There is no intended comparison between the two arms. The literature lacks solid historical control data in this population. One of the reasons for accruing patients to the control arm is to further define the progression rate in a control population.

The primary endpoint is 1-year progression free survival (PFS) rate from start of WT-1 vaccine. Patients will be randomized according to the randomization procedure in Section 15.2 at the time of enrollment on the vaccine study which is after completion of multimodality therapy. PFS will be calculated from the time of randomization to first evidence of disease recurrence or death of any cause. Based on prior multicenter trials of neoadjuvant chemotherapy followed by extrapleural pneumonectomy and hemithoracic radiation (see table below), the 1-year PFS after completion of multimodality therapy is expected to be 50%. An improvement in 1-year PFS to 70% would be of interest for the vaccine arm (Arm A).

Author	Country	Year	Study type	N	Med time to recurrence (mo)
Weder ³⁴	Switzerland	2004	Prospective	19	16.5
Rea ³⁵	Italy	2007	Prospective	21	16.3
Weder ³⁶	Switzerland	2007	Prospective	61	13.5
Batirel ³⁷	Turkey	2008	Prospective	20	10
Bolukbas ³⁸	Germany	2009	Prospective	35	15.8
Krug ⁴	US	2009	Prospective	77	10.1

Amended: 7/14/15

MEMORIAL SLOAN-KETTERING CANCER CENTER IRB PROTOCOL

IRB#: 10-134 A(8)

Van Schil ³⁹	EORTC	2009	Prospective	59	13.9
Hasani ⁴⁰	Australia	2009	Retrospective	36	12.5

Therefore a two parallel single-stage design will be employed to assess the primary endpoint of PFS at 1-year in each arm separately. For each arm, a 50% progression-free rate at 12 months is considered not promising, a 70% progression-free rate at 12 months is considered promising, and the probabilities of a type I error (falsely accepting a non-promising therapy) and type II error (falsely rejecting a promising therapy) are set at 0.10 and 0.10, respectively. Thirty-nine patients will be accrued to each arm. All patients who receive at least one vaccination will be considered evaluable in an intent-to-treat analysis. All patients will be followed for a minimum of twelve months. At the end of the trial, if 24 or more patients are progression-free at one year out of a total of 39 patients then that treatment arm will be considered worthy of further investigation. If 23 or fewer patients are progression-free at one year in a given treatment arm then that treatment arm will be declared negative. This design yields at least a 0.90 probability of a positive result if the true progression-free survival is at least 70% and yields a 0.90 probability of a negative result if the true progression-free survival is 50%.

We have included a stopping rule for futility into the trial design (each arm can stop separately). Accrual to an arm will be stopped for futility if:

- >= 7 of the first 10 patients accrued experience progression within 1 year
- >= 10 out of first 20 patients accrued experience progression within 1 year
- >= 14 out of first 30 patients accrued experience progression within 1 year

The trial will not be halted between stopping rule assessments. Accrual to date has been slow (5 patients in one year at MSKCC). The benefit of the stopping rule outweighs the potential for over-accruing patients in between these interim assessments. This design has 7% chance of stopping if true PFS rate is 70% and 75% if true PFS rate is 50%.

A planned interim analysis took place to assess for futility. At the time of this analysis >=10 out of the first 20 patients had experienced progression within 1 year. As a result of these findings, enrollment to the control arm (GM-CSF + Montanide) was recommended to be closed, while enrollment to the study arm continues pending further follow up data. This amendment (6/2015) addresses this change in trial design.

Toxicities will be tabulated according to the NCI Common Toxicity (version 4.0). Immunologic response will be assessed for all patients. Immune responses will be evaluated at baseline and at week 12 by CD4 T cell proliferation, CD4 and CD8 T-cell interferon release. A response will be called positive for reactivity with the test peptides if the result is at least 2 fold higher for the test peptides as compared to the control peptides. Overall survival will be calculated from date of randomization to date of death or last follow-up. Progression free survival will be calculated from date of randomization to date of progression, death or last

MEMORIAL SLOAN-KETTERING CANCER CENTER IRB PROTOCOL

IRB#: 10-134 A(8)

follow-up. Survival distributions for each arm will be estimated using Kaplan-Meier methodology.

Measurement of the tumor marker, SMRP, is an exploratory aspect of this study to determine whether elevating levels on serial measurements correlates with recurrence as determined using traditional CT scan imaging.

Originally, a total of 78 patients were planned for accrual to this study. Due to the interim analysis that led to early closure of the control arm, total sample size was lowered to 60 patients. Enrollment is anticipated to take 6 years. Additional centers will enroll patients on an identical protocol under their own IND, and the data will be pooled with those from MSKCC for the final analysis.

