GM-CSF: GM-CSF has been used in a number of vaccines studies as an immunologic adjuvant with the presumed benefit mediated through effects on dendritic and other antigen-presenting cells. Several human vaccine studies in melanoma and other human malignancies have reported both encouraging immunologic and clinical results. More recently, two melanoma vaccine studies have reported a deleterious effect of GM-CSF when used as a vaccine adjuvant.^{25,26} While it is important to be cognizant of such a potential negative effect, this study uses a different vaccine with a different dose of GM-CSF in a different disease. Other peptide vaccines studies have used GM-CSF as an adjuvant without negative results.^{27,28}

Rationale for study design: We have chosen to test the efficacy of our WT-1 peptide vaccine in MPM patients who have minimal disease burden after completion of multimodality therapy, but remain at exceedingly high risk for recurrence. Designing a clinical trial to show a benefit from a cancer vaccine is notoriously challenging. Single arm studies showing prolonged time to progression or survival are fraught with patient selection bias. The only way to avoid this bias and show that a vaccine has provided a benefit is by conducting a randomized trial. In this case, we chose to study treatment with Montanide and GM-CSF in one arm. Some immunologists would argue that the use of immune stimulants, such as GM-CSF, could provide a non-specific immune response resulting in some anti-tumor effects. Indeed, this has been observed in studies in prostate cancer and melanoma^{29,30}. The other arm will receive treatment with GM-CSF plus more targeted immunotherapy with WT-1 vax/Montanide. Although the size of this randomized phase II trial precludes direct comparison of the two arms, it will provide valuable information regarding the utility of immunotherapy in the adjuvant setting for this disease. If this study yields promising results, a larger randomized phase III trial would be warranted for confirmation of benefit from WT-1 vax.

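### Should the plan add a vaccine-versus-control estimate because the 24-of-39 rule rests on a fixed 50% benchmark with weak historical support?

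*Combined protocol and SAP*

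**What the plan says.** Section 14.0 sets up two separate single-stage assessments. For the null it states: "For each arm, a 50% progression-free rate at 12 months is considered not promising". A rate of 70% is promising, both error rates are 0.10, and an arm succeeds with 24 or more of 39 patients progression-free at one year. From a table of eight studies the section concludes that "the 1-year PFS after completion of multimodality therapy is expected to be 50" per cent, but it also admits: "The literature lacks solid historical control data in this population".

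On the control arm, Section 14.0 states "There is no intended comparison between the two arms" and explains: "One of the reasons for accruing patients to the control arm is to further define the progression rate in a control population". Section 3.0, under the rationale for the design, gives the reason for not comparing: "Although the size of this randomized phase II trial precludes direct comparison of the two arms". It names a larger phase III trial as the next step if results are promising. The only planned survival summary is a Kaplan-Meier curve for each arm.

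After the interim futility look the control arm was closed and the vaccine arm continued. Sections 7.0 and 14.0 reduce the total from 78 to 60. Sections 1.0, 4.1 and part of 14.0 still say 39 per arm.

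**The concern.** The protocol appears to argue against itself. Section 3.0 warns: "Single arm studies showing prolonged time to progression or survival are fraught with patient selection bias". It presents randomisation as the remedy, and Section 15.2 stratifies by surgery type and stage. The vaccine verdict is then reached as if the trial had one arm, against a figure whose basis the protocol itself describes as weak.

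At stake is the real chance of taking an ineffective vaccine forward, which is 10% only if 50% is the true background rate. The early closure adds two worries. Vaccine patients enrolled afterwards have no concurrent controls but count towards the 39. And a control arm closed because many patients progressed will show a rate that is too low on average, which flatters the vaccine when the two curves are viewed together. A supportive difference with a confidence interval, limited to patients randomised while both arms were open, looks like a cheap remedy.

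**Working it through.** **1. The plan's own figures.** Inputs from Section 14.0: n = 39, cut-off 24, null 0.50, target 0.70. Let X be the number progression-free at one year, binomial(39, p).

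- P(X ≥ 24) at p = 0.50 is 0.0998, so a negative result has probability 0.900.
- P(X ≥ 24) at p = 0.70 is 0.906.
- The futility looks (7 of 10, 10 of 20, 14 of 30 progressed) stop with total probability 0.751 at 50% and 0.069 at 70%.

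These match the stated 0.90, at least 0.90, 75% and 7%.

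**2. Sensitivity to the benchmark.** P(X ≥ 24) for an ineffective vaccine, ignoring the futility looks:

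| True background rate | Probability of passing |
|---|---|
| 45% | 0.028 |
| 50% | 0.100 |
| 55% | 0.256 |
| 60% | 0.491 |

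**3. What the Section 14.0 table supports.** Assuming exponential times, a median of m months gives a one-year rate of 0.5^(12/m). The lowest median, 10 months, gives 0.435; the highest, 16.5 months, gives 0.604. Weighting all eight studies by size gives 0.522 over 328 patients. The pass probability is 0.018 at 0.435, 0.157 at 0.522 and 0.512 at 0.604. The extremes come from studies of 20 and 19 patients. The table reports time to recurrence from an origin it does not state, whereas PFS here also counts deaths, so the conversion is only a rough guide.

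**4. Precision of a concurrent contrast.** If all 39 vaccine patients fall within the 60, there are 60 − 39 = 21 controls. With equal allocation until closure, about 21 vaccine patients are concurrent and 39 − 21 = 18 are not. The split is an assumption. The 95% half-width is 1.96 × √(p₁q₁/n₁ + p₂q₂/n₂):

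- 50% v 50%: 1.96 × √(0.25/21 + 0.25/21) = 0.302
- 70% v 50%: 1.96 × √(0.21/21 + 0.25/21) = 0.290

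**5. Bias of that contrast.** Assume the look at 20 closed the control arm, the vaccine arm passed the same look, each arm has one further patient, and the vaccine does nothing. Enumerate the two blocks of ten with fewer than 7 progressions in the first block, then split at 10 or more v fewer than 10 progressions among the 20. At a true 50%:

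- Control, stopped: mean progression-free among 20 is 8.907; adding one patient, (8.907 + 0.5)/21 = 0.448.
- Vaccine, continued: mean is 12.155; (12.155 + 0.5)/21 = 0.603.
- Spurious difference: 0.603 − 0.448 = 0.155.

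At a true 45%, 55% and 60% the spurious difference is 15.5, 16.0 and 17.3 points. The control stop alone accounts for 50 − 44.8 = 5.2 points at a true 50%; the rest comes from the vaccine arm having passed.

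**6. Pooling after closure.** With 21 vaccine patients at 50% and 18 at 45%, 50%, 55% or 60%, the pass probability is 0.058, 0.100, 0.160 or 0.240. The later rates are hypothetical. The documents describe no change of eligibility at closure, and a single-arm rule does not rely on concurrency.

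**The case for a change.** The strongest case for a change is that trial size justifies omitting a test but not an estimate. A formal comparison of 70% with 50% at one-sided 0.10 and 90% power needs 78 per arm, so no one would expect a test. A labelled difference with its interval, however, costs no patients or visits, shows honestly how little the trial can say, and is better than leaving readers to compare two curves by eye. The benchmark also comes from trials that Section 14.0 describes as extrapleural pneumonectomy series, whereas Section 6.1 also admits pleurectomy/decortication and some R2 resections.

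Some of this stands. The 50% is uncertain, the pass probability is sensitive to it, and a low control rate after a futility stop should not be taken at face value. But the proposed estimate answers none of these points. It leaves the 24-of-39 error rate where it was. It cannot show whether 50% is right for untreated patients, because controls receive Montanide and GM-CSF, and Section 3.0 allows that such stimulants "could provide a non-specific immune response resulting in some anti-tumor effects". A caveat naming only the control arm's stopping bias would understate the problem, since selection can act on both arms. A figure centred near +15 points under no effect, chosen after the interim look, could mislead more than two separately reported curves that the plan says are not for comparison.

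**Conclusion.** No change is needed. Judging each arm against a fixed rate is a deliberate trade-off, stated in Sections 3.0 and 14.0 and suited to a trial meant to decide whether a phase III study is worthwhile. The rule is computed correctly. The 50% has a source: eight studies whose size-weighted reading is about 52% if times are exponential, where an ineffective vaccine passes with probability about 0.16 rather than 0.10. The wider range of 0.02 to 0.51 requires the two most extreme small studies to be taken as the truth.

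The contrast offers no dependable gain: a half-width of about 29 to 30 points, and a bias of about +15 to +17 points with no true effect. The half-width rests on an assumed 21 per arm. The bias rests on a control stop at 20, a vaccine arm held to the same look, and one further patient in each. Section 14.0 does not say outright that the first 20 patients were control patients, only that the vaccine arm continued pending follow-up, so the size of the bias is conditional.

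The rest is detail that analysts fill in sensibly. Actual numbers by arm and the closure date can be reported from the trial records, and the leftover 39-per-arm wording is a clerical remnant explained by the change to 60 in Sections 7.0 and 14.0. None of it alters the primary result.

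### The set labelled intent-to-treat needs a first vaccination, but PFS mostly runs from randomisation; the effect on the 24-of-39 rule depends on handling that Section 14.0 does not state

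*Combined protocol and SAP*

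**What the plan says.** All of the relevant text is in Section 14.0 of the combined protocol and SAP.

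- **Analysis set:** "All patients who receive at least one vaccination will be considered evaluable in an intent-to-treat analysis".
- **Clock, operational definition:** "PFS will be calculated from the time of randomization to first evidence of disease recurrence or death of any cause". It is repeated later in the section: "Progression free survival will be calculated from date of randomization to date of progression, death or last" follow-up.
- **Clock, endpoint sentence:** "The primary endpoint is 1-year progression free survival (PFS) rate from start of WT-1 vaccine".
- **Time of randomisation:** "Patients will be randomized according to the randomization procedure in Section 15.2 at the time of enrollment on the vaccine study", so before the first injection.
- **Benchmarks for each arm:** "a 50% progression-free rate at 12 months is considered not promising" and "a 70% progression-free rate at 12 months is considered promising". The two error rates "are set at 0.10 and 0.10, respectively".
- **Decision:** 39 patients are accrued per arm, and an arm is positive if at least 24 of the 39 are progression-free at one year. The futility looks count patients accrued, not patients vaccinated.

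I found no statement of how a never-vaccinated patient counts in the 24-of-39 rule, whether such patients are replaced, how many are expected, or the longest allowed gap from randomisation to first injection.

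**The concern.** An intent-to-treat set contains everyone randomised. This one requires a first vaccination, so it is a treated-patient set under another name. Combined with a clock that starts at randomisation, it leaves a gap: an event between randomisation and first injection belongs to the endpoint, but its patient does not belong to the set.

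The mismatch matters more here than in a comparative trial. Each arm is judged on its absolute rate against fixed benchmarks, and the plan intends no comparison between arms. Blinding and randomisation therefore do not cancel a shift in that rate. The pass mark is also tight: 24 successes pass and 23 fail.

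**Working it through.** **Inputs from Section 14.0:** n = 39 per arm, bar 24, null rate 0.50, alternative 0.70, both errors 0.10. **Assumed, because the documents give no figure:** the number of non-starters (1 to 3 shown) and their own 1-year PFS (0%, 25%, or the same as treated patients).

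**Plan's figures reproduced.** Exact binomial, single-stage rule:
- P(X ≥ 24 | n = 39, p = 0.50) = 0.0998, against the stated 0.10.
- P(X ≥ 24 | n = 39, p = 0.70) = 0.906, against the stated 0.90 or more.

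All results below also leave out the futility looks. With those looks applied, the false-positive chance is 0.090 before any non-starter is considered.

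**Case 1: non-starters are replaced until 39 are vaccinated.** With m non-starters whose own rate is q, and a rate of 0.50 over all 39 + m randomised, the rate among the vaccinated is

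p = [0.50 × (39 + m) − q × m] / 39.

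For m = 2 and q = 0, p = 20.5/39 = 0.526.

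| m | P(X ≥ 24), q = 0 | P(X ≥ 24), q = 0.25 | P(X ≥ 24), q = 0.50 |
|---|---|---|---|
| 1 | 0.131 | 0.115 | 0.0998 |
| 2 | 0.168 | 0.131 | 0.0998 |
| 3 | 0.212 | 0.149 | 0.0998 |

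**Case 2: 39 randomised, k dropped, bar reset to the smaller n.** For k = 2, n = 37. The smallest bar with type I error at or below 0.10 is 23, because P(X ≥ 23 | 37, 0.50) = 0.094. An arm with 23 successes then passes, and its reported rate moves from 23/39 = 59.0% to 23/37 = 62.2%. If both dropped patients fail and the rate over all 39 is 0.50, the rate among the vaccinated is 19.5/37 = 0.527 and P(X ≥ 23 | 37, 0.527) = 0.162.

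**Case 3: 39 randomised, k dropped, bar kept at 24.** A dropped patient cannot add a success.
- *False-positive chance*, if all k fail and the rate over all 39 is 0.50: p = 19.5/(39 − k), and P(X ≥ 24 | 39 − k, p) = 0.097, 0.093, 0.089 for k = 1, 2, 3.
- *Power*, if the dropped patients would have had the same 70% rate as treated patients: P(X ≥ 24 | 39 − k, 0.70) = 0.863, 0.807, 0.737 for k = 1, 2, 3, against 0.906.

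**All 39 randomised counted, no replacement.** The calculation is again P(X ≥ 24 | 39, p), giving 0.0998 and 0.906. The sample size and the bar do not change.

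**The case against.** A reader might infer that the exclusion inflates the rate the decision rests on, and so raises the type I error. The documents do not support that as a flat statement. Read literally, the rule needs 24 successes from 39 accrued patients. Removing a failure leaves 23 successes at 23, and Case 3 shows the false-positive chance going slightly down. Inflation needs replacement or a reset bar, and the plan states neither. It also needs non-starters to do worse than treated patients. That is plausible for early progression or death but less clear for withdrawal.

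Three further points count on that side:

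- The endpoint sentence starts the rate at the start of vaccine, which does fit a vaccinated set.
- The evaluability sentence may be meant to keep patients who stop before six injections. Exclusion of the never-vaccinated is implied by it, not spelled out.
- The gap may be short. Randomisation follows confirmed eligibility (Section 15.2), baseline tests fall within 2 weeks and the CT within 4 weeks of the first vaccination (Section 8.0), and no further CT is scheduled until week 12.

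These points make the inflation claim conditional. They do not remove the mismatch. The start-of-vaccine sentence sits in the same paragraph as the randomisation clock, so it adds a conflict. If everyone randomised were meant to count, requiring at least one vaccination would serve no purpose. A short gap limits the number of patients affected, but no maximum is given.

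**Conclusion.** The concern holds in a conditional form. The analysis set does not match the randomisation clock, the intent-to-treat label is wrong for it, and Section 14.0 gives two time origins for the primary endpoint. The reported 1-year rate can be biased upward against the benchmarks if non-starters do worse than treated patients.

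The documents do not fix the direction of the effect on the decision. For 1 to 3 non-starters, the false-positive chance can be as high as 0.131 to 0.212 (replaced, all fail), or 0.115 to 0.149 if their own rate is 25%. It stays at 0.0998 if they are replaced and do as well as treated patients. With the bar held at 24 of 39 randomised, it is 0.097 to 0.089, and the possible cost is power, down to between 0.863 and 0.737. All of these rest on an assumed number of non-starters and concern the single-stage rule alone. The text should be settled before the final count, because the choice of handling could otherwise be made with the results in view.

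**What to change.** Use one time origin throughout Section 14.0.

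**Preferred.**
- Keep randomisation as the origin, with registration as the origin for vaccine patients enrolled after the control arm closed.
- Make all randomised or registered patients the denominator of the primary count, without replacement.
- Follow never-vaccinated patients for progression and death. Count one without a documented progression-free year as not progression-free.
- Report the set with at least one vaccination as a sensitivity analysis under its own name.

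The rule of 24 of 39 then keeps type I error 0.0998 and power 0.906.

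**Otherwise.** Start PFS at the first vaccination in every sentence, call the set treated patients, drop the term intent-to-treat, and state whether non-starters are replaced. Define vaccination for both arms, since the endpoint sentence names a product that the control arm does not receive.

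**Cost.** A few sentences in Section 14.0. The preferred route also means follow-up of a few more patients and probably a slightly lower reported rate.

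### The stated power of at least 0.90 leaves out the futility rule in the same section; with that rule, power is 0.88 and type II error 0.12

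*Combined protocol and SAP*

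**What the plan says.** Section 14.0 (Biostatistics) describes the primary analysis in these words: "a two parallel single-stage design will be employed to assess the primary endpoint of PFS at 1-year in each arm separately". In each arm "a 50% progression-free rate at 12 months is considered not promising" and "a 70% progression-free rate at 12 months is considered promising". Type I error and "type II error (falsely rejecting a promising therapy) are set at 0.10 and 0.10, respectively". The sample size is fixed: "Thirty-nine patients will be accrued to each arm". An arm is positive if at least 24 of the 39 are free of progression at one year and negative otherwise. The operating claim follows: "This design yields at least a 0.90 probability of a positive result if the true progression-free survival is at least 70" per cent, with a matching 0.90 probability of a negative result at 50%.

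The next paragraph adds a futility rule as part of the trial design, applied to each arm separately. "Accrual to an arm will be stopped for futility if" at least 7 of the first 10, at least 10 of the first 20, or at least 14 of the first 30 patients progress within a year. The rule gets its own operating figures: "This design has 7% chance of stopping if true PFS rate is 70% and 75% if true PFS rate is 50" per cent. Power and type II error are not restated with the rule in force.

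**The concern.** An arm with a true rate of 70% can have a poor early run, cross a boundary and be closed, although it would have recovered to 24 of 39. Every such path is a positive result lost, so a futility rule that is followed can only lower power. Power for 24 of 39 alone is only just above 0.90, which leaves little to give away. The plan's own 7% stopping probability at 70% shows that the looks are not free.

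What is at stake is how a negative vaccine arm is read. The plan tells the reader that a promising treatment is missed 10% of the time. If the futility rule is followed, the figure is higher, and nothing in the section gives it.

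**Working it through.** **Inputs, all from Section 14.0.** Not-promising rate 0.50; promising rate 0.70; 39 patients per arm; positive if at least 24 are progression-free, that is, at most 15 progressions; stop at ≥7/10, ≥10/20 or ≥14/30 progressions. Patients are treated as independent with a known one-year outcome, and a stopped arm counts as not positive.

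**Step 1: reproduce the plan's power, without looks.** With X the number progression-free, X ~ Binomial(39, p):

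- P(X ≥ 24 | p = 0.70) = 0.9056
- P(X ≥ 24 | p = 0.50) = 0.0998, so P(negative) = 0.9002

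These are the stated 0.90 and 0.90. They belong to the single-stage rule alone.

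**Step 2: reproduce the plan's stopping figures.** Let f(n, k) be the probability of k progressions among the first n patients with no boundary yet crossed. Then

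f(n, k) = p · f(n−1, k) + (1−p) · f(n−1, k−1), with f(0, 0) = 1.

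At n = 10, 20 and 30, the mass with k ≥ 7, 10 and 14 respectively is counted as stopped and set to zero.

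| True PFS | Stop at 10 | Stop at 20 | Stop at 30 | Total | Plan |
|---|---|---|---|---|---|
| 70% | 0.0106 | 0.0410 | 0.0169 | 0.0685 | 7% |
| 50% | 0.1719 | 0.4231 | 0.1560 | 0.7510 | 75% |

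Both totals agree with the plan, so the boundaries and the model are those the authors used.

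**Step 3: power with the looks.** P(positive) is the sum of f(39, k) over k ≤ 15.

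| | Looks ignored | Looks applied | Plan |
|---|---|---|---|
| P(positive) at 70% | 0.9056 | 0.8818 | at least 0.90 |
| Type II error | 0.0944 | 0.1182 | 0.10 |
| P(positive) at 50% (type I error) | 0.0998 | 0.0901 | 0.10 |
| P(negative) at 50% | 0.9002 | 0.9099 | 0.90 |

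A simulation of 1,000,000 arms at 70% gave power 0.8819.

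**Step 4: where the power goes.** Adding the looks one at a time at 70%:

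- none: 0.9056
- look at 10: 0.9008 (loss 0.0048)
- looks at 10 and 20: 0.8844 (further loss 0.0164)
- all three: 0.8818 (further loss 0.0026)

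The total loss is 0.9056 − 0.8818 = 0.0238, most of it at the 20-patient look. It is smaller than the 0.0685 stopping probability because 0.0685 − 0.0238 = 0.0447 of the stopped paths would have missed 24 of 39 anyway. Power therefore cannot be recovered from the disclosed 7% by subtraction: 0.906 − 0.07 would give about 0.84, which is also wrong.

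**Step 5: could another reading rescue 0.90?** With strict boundaries (more than 7, 10 and 14), power is 0.9010, but the stopping probabilities become 2.7% and 60.8%. That contradicts the stated 7% and 75%, so the reading is excluded.

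**The case against.** The strongest reply is that the 0.90 sentence is correct for the rule it directly follows. The plan names a single-stage design, gives the 24-of-39 cut-off and states its power; the futility rule opens a new paragraph with its own figures. On that view only a combined figure is missing. That is a fair account of how the text came about, but the plan says the futility rule is part of the trial design and uses the same subject, this design, for both sets of figures. Both cannot describe one design.

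Second, the section does not say that the rule is binding or that a stopped arm is declared negative, and it accepts that accrual runs on between assessments. An arm that crossed a boundary but still reached 39 patients and was judged on 24 of 39 would put power between 0.882 and 0.906. This stands as a caveat: 0.882 is the value when the rule is always followed. But the stopping instruction is worded as mandatory, the 7% and 75% assume it is followed, and the plan records that meeting the 20-patient boundary led to a recommendation to close the control arm.

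Third, the effect is small. Power is 1.8 points under 0.90, it is 0.906 if the true rate is 71%, and Section 14.0 itself concedes that historical control data are weak. This also stands, and it limits the point to a correction of the text. The lower type I error is no complaint against the design.

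**Conclusion.** The concern holds. For the design as written, the probability of a positive result at a true one-year PFS of 70% is 0.882, not at least 0.90. The type II error is 0.118, not 0.10: about 18% higher in relative terms (0.118/0.10). Type I error is 0.090, inside the 0.10 set.

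This rests on three assumptions: the futility rule is followed at all three looks, a stopped arm counts as not positive, and each arm would otherwise reach 39 patients with a known one-year outcome. If the rule is not always followed, power lies between 0.882 and 0.906. The figures are per arm for the 39-patient plan. They do not describe the study after control-arm closure and the reduction to 60 patients in total, for which the section gives no new operating characteristics. The error lies in a reported figure; it does not make the sample size or the cut-off unsound.

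**What to change.** In Section 14.0, replace the power sentence with one that covers the whole design, for example: With the futility rule applied, the probability of a positive result in an arm of 39 is 0.88 if true one-year PFS is 70% and 0.09 if it is 50% (type II error 0.12, type I error 0.09); without the futility looks these probabilities are 0.91 and 0.10.

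Adjust the statement that both errors are set at 0.10 to agree. Add that a stopped arm counts as not positive or, if the rule is meant to be advisory, say so and give the range 0.88 to 0.91. State that the figures refer to the design before the control arm was closed.

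The cost is a few lines of text and a slightly less favourable stated power. No patients are added, and neither the cut-off nor the boundaries change.
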